5.2. Analysis

Nonparametric data such as those resulting from the VAS assessments from the two groups will be compared using the Mann–Whitney U test. The Student's *t*-test will be used to compare normally distributed continuous variables. A *p* value of less than or equal to 0.05 will be considered statistically significant.

6. Data and Safety Monitoring

All subjects enrolled in this study will receive at least one of two types of treatment for their PDPH. Both the EBP and SPG block are low-risk procedures that can be and are routinely performed in an office setting on outpatients in our pain clinic at the New Jersey Pain Institute. Furthermore, neither of these techniques are experimental; rather, their methods are well documented in literature and are common procedures in the pain medicine field.

Subjects who undergo the procedures within this study will have additional monitoring as opposed to patients who undergo the same procedures outside of this study. Patients in this study will receive two follow-up phone calls to assess their symptoms and to expedite the availability of any additional procedures that need to be performed. These telephone calls will also serve to inform the SIs and PI if the patients are experiencing any undue and unexpected harms as a result of this study. As all of the investigators in this study are in the department of anesthesia, they are the best equipped to identify potential side effects and treatment.

All subjects enrolled in this study will be given a contact sheet including phone numbers by which they may reach the PI, emergency room, the pain clinic, and the Pain Medicine

physician-on-call who, as previously stated, is available continuously by mobile telephone.

7. Reporting Results

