1.1. Objectives

- 1.1.1. To compare subjects who present with PDPH and are randomized into one of two treatment groups whether the SPGB technique is not inferior to the traditional EBP in treating their symptoms.
- 1.1.2. To follow subjects who initially present with PDPH to determine the efficacy of either technique in maintaining a symptom-free period.
- 1.1.3. To compare patients' experiences with the SPGB as compared to the EBP.

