The EBP has traditionally been the definitive mode of treatment in patients with PDPH. This intervention involves the autologous transfusion of a patient’s blood from a sterile peripheral site into the epidural space. Several studies have established the EBP as standard of care for PDPH. A randomized, controlled clinical trial has showed that EBPs resolve PDPHs after one week in 84% of patients compared to 14% with placebo (7). Another prospective, randomized, double-blinded trial compared EBP to conservative management (fluid replacement, non-steroidal anti-inflammatory drugs, and caffeine) for the treatment of PDPH. (8). These authors found that when treated conservatively patients with PDPH noted little to no change in headache, as reported on a visual analog scale (VAS). Their headaches rated 8.2 ± 1.4 both before and after treatment. In the group who received an EBP, patients reported a decrease in headache from 8.0 ± 1.6 to 0.7 ± 0.16 . The authors further state that “The epidural blood patch represents the first choice treatment of PDPH no matter the etiology, being significantly superior to the conventional treatment which did not affect pain scores” (8). These studies have helped establish the EBP as a standard of care for PDPH. It now appears as a listed treatment for PDPH in common physician reference resources such as UpToDate® (Waltham, MA) (9).

Originally, the EBP was thought to act through a tamponade effect, plugging the dural defect and preventing the further leakage of CSF. As noted above, this is unlikely the true mechanism as patients often report immediate relief, which could not be explained by cessation of the minute flow of CSF. The more contemporary explanation is that the EBP does in fact plug the dural tear, but in doing so, it prevents the equilibration of CSF pressure with the atmospheric pressure. Injection of blood into the epidural space immediately raises

the CSF pressure within the closed spinal canal space and thus causes reflex cerebral vasoconstriction. Consequently, subdural venous collapse is restored and the headache subsides.

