3.2. Study Design

3.2.1. Type

This is a non-inferiority trial comparing the SPGB to the EBP for the treatment of PDPH. The study is not blinded to the subject or investigator. Due to the nature of the procedure and the anatomical site of intervention, both will know which method they are receiving or delivering. We acknowledge this as a limitation of our study but reiterate that blinding one or both parties is not feasible.

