For patients randomized to group 2 (SPGB), the symptoms in Table 8 will be assessed and graded at 30 min post-procedure. If this treatment does not decrease the patient's "orthostatic headache" severity past the pre-treatment score, then the SPGB will be performed for a second time. The symptoms will be graded again 30 min after the second block. If the "orthostatic headache" severity score is still unchanged, then a SPGB will be performed for a third time. If the "orthostatic headache" severity score remains unchanged at the 30 min mark following the third SPGB, the procedure will be considered a failure and conservative measures or an EBP will be offered to the patient.

If the first, second or third SPGB succeeds in decreasing the "orthostatic headache" severity score at 30 min post-procedure, the symptoms in Table 8 will be assessed and graded again at 60 min post-procedure. In all cases, the same symptoms will be assessed at 24 and 48 hours post-procedure in the manner noted above. If patients in any group on telephone interview note dissatisfaction with the alleviation of the symptoms or if the symptoms return, they will be given the option of arriving at the Pain Clinic at the New Jersey Pain Institute during normal clinic hours or to the emergency room (ER) after hours. At that time, they will be given the option of an EBP, SPGB or medical management. This is the same as what would be offered if a patient underwent treatment for a PDPH outside of this study and had symptoms return afterward.

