3.6. Sample Size Justification

We derive data for calculation of the sample size from the prior studies noted above. In the control group (Table 7, Group 1, EBP) we predict a success rate of 84% as noted by van Kooten et al. (7). In the treatment group (Table 7, group 2, SPG block) we predict a success rate of 68% based on our pilot study (15). If therefore there is a true 16% (84% - 68%) in favor of the EBP group then 210 subjects are required to be 90% certain that the upper limit of a one-sided 95% confidence interval will exclude a difference in favor of the EBP group of more than 33%. This calculation was performed using the formula below (Table 9 and Equation) using an online calculator <https://www.sealedenvelope.com/power/binary-noninferior/>).

Our chosen non-inferiority limit d of 33% means that we believed saving 67% (100% – 33%) of patients from the invasive EBP in favor of the non-invasive, cost-effective SPG block would be clinically relevant.

Table 9. Values used for determination of sample size

Variable	Description	Value
n	sample size	210
ϕ^{-1}	cumulative distribution function of a standardized normal deviate	n/a
α	significance level, alpha	0.05
β	false negative rate, beta, where power $(1 - \beta) = 0.90$	0.10
π_s	success rate in control group	0.84
π_e	success rate in treatment group	0.68
d	non-inferiority limit	0.33

Equation. Sample size calculation for a binary outcome non-inferiority trial

$$n = \left(\phi^{-1}(\alpha) + \phi^{-1}(\beta) \right)^2 \times \frac{\pi_s \times (100 - \pi_s) + \pi_e \times (100 - \pi_e)}{\pi_s - \pi_e - d^2}$$

4. Study Variables

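### The trial is declared and sized to show non-inferiority on a success proportion, but Section 5.2 plans only difference tests and never analyses that endpoint

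*Combined protocol and SAP*

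**What the plan says.** Objective 1.1.1 asks "whether the SPGB technique is not inferior to the traditional EBP in treating their symptoms", and Section 3.2.1 states: "This is a non-inferiority trial comparing the SPGB to the EBP for the treatment of PDPH".

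Section 3.6 predicts success in 84% with EBP and 68% with SPGB. It requires that the "upper limit of a one-sided 95% confidence interval will exclude a difference in favor of the EBP group of more than 33" percentage points, with 90% power and 210 subjects. Section 5.1 speaks of 210 completers in each group.

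Section 5.2 is the whole analysis section in the available text. It has three elements. VAS-type data: "Nonparametric data such as those resulting from the VAS assessments from the two groups will be compared using the Mann–Whitney U test". Normally distributed continuous variables: Student's t-test. Threshold: a p "value of less than or equal to 0.05 will be considered statistically significant".

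On what counts as success, Section 3.2.3 defines failure for SPGB only. If the orthostatic score is unchanged after a third block, "the procedure will be considered a failure and conservative measures or an EBP will be offered to the patient". Patients in either group who are later dissatisfied or relapse may return, and then "they will be given the option of an EBP, SPGB or medical management". The last scheduled assessment is at 48 hours.

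The source of the 84% is given in Section 2: "EBPs resolve PDPHs after one week in 84% of patients compared to 14% with placebo". The 68% is 19 of 28 pilot patients who had relief; the other 9 are described, again with reference to one week, as needing an EBP.

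**The concern.** The design sections and the analysis section answer different questions. A Mann–Whitney or t-test asks whether the arms differ. Objective 1.1.1 asks whether SPGB is worse by less than a stated amount. Section 5.2 names no analysis of a proportion and no confidence limit, and it does not refer to the 33-point margin. The endpoint that set the sample size therefore has no planned analysis.

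A reader who tries to repair this by borrowing the rule from Section 3.6 finds that success is not defined in a way that applies to both arms, at a time when patients are assessed. The definition, the time point and the handling of further procedures could then be settled after data are seen, in a trial where neither patient nor investigator is blinded (Section 3.2.1).

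**Working it through.** **1. The plan's sample size.** Inputs from Section 3.6: 0.84, 0.68, margin 0.33, one-sided α 0.05, power 0.90. Equal allocation is assumed, as no ratio is stated.

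n per arm = (1.645 + 1.282)² × (0.84×0.16 + 0.68×0.32) / (0.16 − 0.33)² = 104.3, so 105 per arm and 210 in total.

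The 210 is therefore a total, obtained from a margin test on a difference of proportions. Results are shown below for 105 per arm and for 210 per arm, the reading in Section 5.1.

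**2. Can a difference test stand in for the margin test?** Section 5.2 names no test of proportions, so one is used here for illustration only. The conflict rate for Mann–Whitney on VAS scores cannot be computed from the documents.

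SE = √[(0.84×0.16 + 0.68×0.32)/n] = 0.0579 at n = 105 and 0.0409 at n = 210. Both results occur when the observed difference exceeds 1.96×SE and also lies below 0.33 − 1.645×SE. With a true difference of 0.16:

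- 105 per arm: observed difference between 0.113 and 0.235, probability 69%.
- 210 per arm: between 0.080 and 0.263, probability 97%.

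A single example is 88/105 against 71/105. The difference is 16.2 points and p = 0.006 (pooled z-test). The upper limit is 0.1619 + 1.645×0.0581 = 0.2575. SPGB is significantly worse and also within the margin.

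**3. Can the Section 3.6 rule be applied as it stands?**

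- Failure is defined for SPGB only, at 30 minutes after the third block, as no change in score. A fall from 8 to 7 is not a failure. EBP has no counterpart.
- The 84% is resolution of headache; the 68% is relief, with no EBP needed. Both refer to one week, whereas assessment ends at 48 hours.
- An EBP given after failed SPGB is, by the wording of Sections 2 and 3.2.3, not an SPGB success. The documents leave open how to count later procedures after initial relief, and later procedures in the EBP arm.

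**4. How much the open part could matter (assumed shares).** Put the true rates at the margin, 84% and 51%. Let a share r of non-successes in both arms receive a further procedure, with 84% of them relieved, and credit that relief to the assigned arm.

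Apparent EBP = 0.84 + 0.16×r×0.84; apparent SPGB = 0.51 + 0.49×r×0.84. The probability of declaring non-inferiority comes from exact enumeration of both binomials, with the rule difference + 1.645×SE < 0.33:

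| r | EBP | SPGB | 105 per arm | 210 per arm |
|---|---|---|---|---|
| 0 | 0.840 | 0.510 | 4.8% | 4.9% |
| 0.25 | 0.874 | 0.613 | 33% | 53% |
| 0.50 | 0.907 | 0.716 | 84% | 98% |

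**5. Power of the margin test.** Φ[(0.33 − gap)/SE − 1.645]:

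| EBP vs SPGB | 105 per arm | 210 per arm |
|---|---|---|
| 84% vs 68% | 90% | 99% |
| 84% vs 60% | 45% | 69% |
| 84% vs 55% | 16% | 24% |

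**The case against.** The best defence is that Section 3.6 already contains the rule: the measure, the direction, the margin and the confidence level. That is correct, and a reader who inferred that the plan has no decision rule would be wrong. But the rule is stated to justify the sample size, Section 5.2 does not refer to it, and the success it needs is not defined for both arms.

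A reader might also infer that Section 5.2 would produce false claims of non-inferiority from a non-significant p-value. This is not shown. With the proportion test as stand-in, the probability of a non-significant result that also fails the margin is 0.0000 at both sample sizes, for EBP at 84% and SPGB at 51%, 68% or 76%. The case rests on the objective having no analysis.

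A third tempting reading is that relief from a rescue EBP would be credited to SPGB. The documents point the other way. Section 3.2.3 calls the procedure a failure before the EBP is offered, and Section 2 treats avoiding an EBP as the pilot's benefit. Crediting the SPGB arm alone would give 54% and 98% at 105 per arm for r = 0.25 and 0.50. Later procedures are open to both groups, however, so the two-arm figures of 33% and 84% are the fairer illustration. The documents also do not show how many such procedures would fall within 24 to 48 hours.

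Finally, Section 5.2 does suit hypothesis 1.2.3, since less discomfort with SPGB is a hypothesis of difference.

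**Conclusion.** The point stands. In the available text (the questionnaire cited as Attachment 1 and one figure are not visible), Section 5.2 neither analyses the endpoint that sized the trial nor yields a non-inferiority conclusion for objective 1.1.1. The sample size arithmetic is not at fault.

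The 69% and 97% assume the plan's own rates, equal allocation and a test of proportions that Section 5.2 does not name. They show that the two rules routinely give different messages, and the plan does not say which governs. The 33% to 98% range depends on assumed shares of further procedures. It shows only that an unwritten counting rule can move the error rate far from 5%.

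The choice of cut-off and time point is a matter of judgement. Leaving them unstated is the defect. The justification of the 33-point margin is a separate question and is taken here as written.

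**What to change.** In Section 5.2:

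- Name one binary primary endpoint, defined identically in both arms from the orthostatic headache VAS already recorded, at one scheduled time (24 or 48 hours). Fix the cut-off before data are seen, and say from which block the time runs when SPGB is repeated.
- Estimate EBP minus SPGB, and declare non-inferiority only if the upper one-sided 95% limit is below the plan's 33 points.
- State one counting rule for both arms: a further PDPH procedure beyond the assigned treatment before that time is not a success. Repeat SPGBs under Section 3.2.3 belong to the assigned treatment. The rule is for analysis only and leaves the care offered unchanged.
- Label the VAS comparisons secondary (Mann–Whitney may stay), and keep the difference test for procedure comfort.

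The cost is protocol wording and one data-sheet field for later procedures. No added recruitment is needed if 84% and 68% hold for the chosen endpoint. Those are one-week figures, though, and a strict cut-off such as VAS 0 could widen the gap, with the loss of power shown in step 5. The planning rates, and if necessary the sample size, should be restated for the endpoint chosen.

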7.1. Individual Results

The only laboratory tests that may be performed are a urine pregnancy test and a platelet count as part of the exclusion criteria (Table 6). Both of these tests are frequently performed on patients in the hospital. If this test was already performed before the patient was enrolled in the study, the physician who ordered the test will be responsible for notifying and counseling the patient. If the test is performed after enrollment in the study, in the case of an unexpected result, namely a positive pregnancy test or a low platelet count, the patient will be notified immediately after the PI or SI views the result. The patient will be excluded from the study and counselled about the ramifications of the results. These laboratory tests will be performed using the same equipment and methods that are used for all patients at Robert Wood Johnson University Hospital.

7.2. Aggregate Results

Aggregate results will be available after statistical analysis. Subjects may contact the PI to view or learn about the aggregate results after the study has been completed. Subjects may be provided with copies of abstracts or directions on how to retrieve the data resulting from this study. Any study data so released to the subjects will be anonymized such that no protected health information is traceable from those data.

